5.0 Enrollment/Randomization

Assignment to treatment order will be randomized and blinded to the investigators and subjects. Subjects will be randomly assigned to drug order using a permuted-block randomization algorithm. [name], study biostatistician, will provide an allocation schedule. Vanderbilt Investigational Drug Services (IDS) will be responsible for the storage, preparation, and labeling of all investigational agents and for maintaining accurate drug storage and dispensing logs. The Clinical Research Pharmacist will devise standard operating procedures for the pharmacy to follow with regard to preparing, labeling, blinding, and dispensing study drug.

After subjects have been consented and screened, the investigator or research nurse will fax a copy of the consent form and a prescription containing check boxes for the inclusion and exclusion criteria to Vanderbilt IDS. The pharmacist will confirm that consent was obtained and the subject met entry criteria, assign the subject a randomization number, and provide the investigator with labeled study drug as indicated in the protocol. An extra label containing the randomization number will be attached to each study drug. The investigator will affix this extra label to the subject's records. The Investigational Pharmacy will retain a secure set of sealed envelopes containing the treatment assignment. These will be opened in the event of a clinical scenario which necessitates unblinding, as determined by the PI and the DSMC (see Data and Safety Monitoring Plan). Subjects randomized who do not complete the whole protocol for any reason will be replaced.

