1. A nurse or physician will be present at all times during the study days.

- 2. Medication withdrawal (hypertensive subjects): Anti-hypertensive medications will be discontinued three weeks prior to the study day to avoid confounding effects on sEH activity or EETs. We have excluded individuals with resistant hypertension to minimize risk. Whenever appropriate, medications will be tapered before they are discontinued. During the washout period, BP will be measured every one to three days. If at any time the seated systolic BP is >170 mmHg or the seated diastolic BP >110 mm Hg or if a hypertensive subject develops symptoms of high BP regardless of the pressure, that subject will be discontinued from the study and his or her anti-hypertensive medications will be restarted. In our experience, approximately five percent of enrolled subjects may be excluded by these BP criteria. Excluded subjects will be replaced.
- 3. Subjects with a history of a hematocrit less than 35% will be excluded from study.
- 4. Only trained investigators will complete adipose and muscle tissue biopsies. We will use sterile technique to minimize the risk of infection, and local anesthesia (lidocaine) will be used to minimize pain. We will monitor subjects for one hour after the biopsies.
- We will monitor glucose concentrations frequently during and immediately after hyperinsulinemic-euglycemic clamps. Should hypoglycemia occur, we will administer glucose.
- 6. We have limited the duration of GSK2256294, and we are excluding participants with a history of cancer or precancerous lesions. We are requiring that subjects be current with American Cancer Society Guidelines for the Early Detection of Cancer and also have PSA screening. We are excluding smokers.
- 7. We will monitor subjects actively for new adverse events using a standard questionnaire.

Should any adverse effects of GSK2256294 become known during the study, we will notify the IRB, we will revise the protocol and consent form as appropriate, and we will advise and re-consent study participants

8.0 Reporting of Adverse Events or Unanticipated Problems involving Risk to Participants or Others

All protocols will be reviewed and approved by the Vanderbilt Institutional Review Board (IRB) before any subject is enrolled. The Principal Investigators will closely oversee the protocol in conjunction with the dedicated research nurse and Co-investigators.

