Soluble Epoxide Hydrolase Inhibition and Insulin Resistance NCT03486223

Statistical Analysis plan from IRB approved version dated Date 8/11/2021

Statistical Analysis Plan:

The primary analysis will focus on the effect of GSK2256294 versus placebo on insulin sensitivity. Secondary endpoints will include the effect of GSK2256294 on insulin-stimulated FBF and renal blood flow; insulin-stimulated AKT phosphorylation in muscle and adipose tissue; tissue CD31 and VEGF expression; insulin-stimulated suppression of hepatic glucose production; plasma, muscle, adipose tissue sEH activity and EETs; and tissue and circulating adipokines and cytokines.

Sample Size and Power Calculation: In our prior study of the relationship between EPHX2 Arg287GIn genotype and insulin sensitivity in obese individuals the insulin sensitivity index was 8.24±4.6 mg/kg/min per μ U/mL*100 (mean±SD) in carriers of the 287GIn allele versus 3.54±1.3 mg/kg/min per μ U/mL*100 in Arg/Arg homozygotes. Conservatively assuming a correlation of 0.5 between two measures of insulin sensitivity in the same subject, the study can detect a within-subject difference of 3.76 (80% of the above difference) or larger (with an SD for the within-subject difference of 4.6) with 80% power and 0.05 type 1 error rate with 34 subjects. The sample size was chosen to allow us to detect effects of treatment within racial or gender group. We need 16 per group to have 86% power to detect difference in insulin sensitivity noted above. Moreover, with 34 subjects, we have 80% power to detect a change in insulin-stimulated FBF of 0.9 mL/min/100 mL in the cross-over study, assuming a within-subject correlation coefficient of 0.5. We will have 80% power to see an increase in insulin signaling (ratio of pAKT to AKT) of 0.07 (0.91±0.13 versus 0.84±0.13 in Arg/Arg).

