Data Analysis Plan: For the within-subject comparison of GSK2256294 versus placebo, we will use either a paired t-test or Wilcoxon-signed rank test. We do not expect a carry-over effect with the eight-week period between study days. Nevertheless, we will test for a carryover effect using the T-test approach proposed by Jones and Kenward. Should a carry over effect exist, we will either use period one data to estimate the treatment effect, or estimate the treatment effect using data from both periods with the understanding that the potential carry over effect may negatively bias the estimate of the treatment difference. Our conservatively planned sample size will help preserve study power. Although we also do not anticipate a period effect, we will use the T-test approach of Hills and Armitage to test for one.

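### The treatment comparison leaves out the randomised drug order and the period test leads to nothing; a period-adjusted contrast is a cheap improvement, not a correction of an error in the primary result

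*SAP*

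**What the plan says.** Drug order is the randomised factor. Protocol section 5.0 (Enrollment/Randomization) states: "Subjects will be randomly assigned to drug order using a permuted-block randomization algorithm". It does not mention stratification by race or gender.

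The SAP's Data Analysis Plan names one treatment comparison: "For the within-subject comparison of GSK2256294 versus placebo, we will use either a paired t-test or Wilcoxon-signed rank test". It contains no period or sequence term. On period effects it says: "Although we also do not anticipate a period effect, we will use the T-test approach of Hills and Armitage to test for one". Nothing is said about what happens if that test is positive. Carry-over is handled differently: there the SAP does name possible responses.

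The SAP's Sample Size and Power Calculation says of race and gender groups: "The sample size was chosen to allow us to detect effects of treatment within racial or gender group", and then: "We need 16 per group to have 86% power to detect difference in insulin sensitivity noted above". The Data Analysis Plan specifies no subgroup test.

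**The concern.** In a two-period crossover, any general change between period 1 and period 2 enters each subject's drug-minus-placebo difference with a sign set by drug order. A paired test treats that change as noise. With equal numbers in the two orders it cancels from the mean but still inflates the SD of the differences, so the test becomes conservative and loses power. With unequal numbers it also moves the estimate in that trial.

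A period test without a consequence adds a further gap. If it is positive, the analysts must choose a response after seeing the data.

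Power is at stake for endpoints and groups with little to spare: secondary endpoints, a primary effect smaller than planned, and the race and gender groups for which the SAP claims 86% power.

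**Working it through.** **Inputs.** From the SAP's Sample Size and Power Calculation: effect 0.8 × (8.24 − 3.54) = 3.76; SD 4.6; correlation 0.5; alpha 0.05 (taken as two-sided); 34 subjects overall and 16 per subgroup; pAKT/AKT difference 0.07 with SD 0.13. The SD of the difference is √(2 × 4.6² × (1 − 0.5)) = 4.6. For pAKT/AKT, 0.13 is assumed as the SD of the difference (correlation 0.5).

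**Assumed period difference.** Write π for period 2 minus period 1. The documents give no value. I use 0, 0.25 and 0.5 of the SD of the difference: on the primary scale 0, 1.15 and 2.3. The last is large, at 2.3 / 3.54 = 65% of the Arg/Arg mean.

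**The plan's figure first.** Paired t-test, noncentral t with n − 1 df and noncentrality (3.76/4.6) × √n:
- n = 16: 0.817 × 4 = 3.27, power 86.3%. The SAP's 86% reproduces.
- n = 34: 0.817 × 5.83 = 4.77, power 99.6%. The SAP's 80% for these inputs is therefore only a lower bound. The effect with 80% power at 34 is 2.28.

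**Model.** The drug-minus-placebo difference has mean effect + π in one order and effect − π in the other.
- *Paired test.* With balanced orders the variance rises from SD² to about SD² + π². At π = 2.3 the SD becomes √(21.16 + 5.29) = 5.14. Power was simulated with 200,000 trials per fixed split.
- *Period-adjusted contrast.* This is half the difference between orders in the mean of period 1 minus period 2. Its standard error is (SD/2) × √(1/n₁ + 1/n₂) on n − 2 df, and π drops out. At 8:8 it is 2.3 × √(1/8 + 1/8) = 1.15, equal to the paired 4.6/√16.

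**Balanced orders**

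| Case | Paired, π = 0 | Paired, 0.25 SD | Paired, 0.5 SD | Adjusted, any π |
|---|---|---|---|---|
| 17:17, effect 3.76 | 99.6% | 99.5% | 99.2% | 99.6% |
| 17:17, effect 2.28 | 80% | 78% | 73% | 80% |
| 17:17, pAKT/AKT 0.07 | 86% | 85% | 80% | 86% |
| 8:8, effect 3.76 | 86% | 85% | 80% | 86% |

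The paired test's type I error at 8:8 is 5.0%, about 4.4% and about 3.0%. It errs on the safe side.

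**Subgroups if order is not stratified.** The number in each order is then hypergeometric, drawn from a 17:17 trial. Power at 3.76, averaged over splits:

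| n | Paired, π = 0 | Paired, 0.25 SD | Paired, 0.5 SD | Adjusted |
|---|---|---|---|---|
| 16 | 86.3% | 84.5% | 78.8% | 84.7% |
| 17 | 88.5% | 86.9% | 81.6% | 87.2% |

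With no period effect, adjustment costs 86.3 − 84.7 = 1.6 points at 16 and 88.5 − 87.2 = 1.3 points at 17. It breaks even at π of about 1.0 to 1.1.

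**One uneven subgroup.** The paired estimate moves by π × (n₁ − n₂)/n.
- At 10:7 the move is 1.15 × 3/17 = 0.20 or 2.3 × 3/17 = 0.41, against a standard error of 4.6/√17 = 1.12. About 49% of subgroups of 17 would split 10:7 or worse.
- At 11:5 and π = 2.3 it is 2.3 × 6/16 = 0.86. Type I error is about 7.5%, and power is 57% or 94% depending on direction, against 80% adjusted. About 8% of subgroups of 16 would split 11:5 or worse.

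**The case against.** The strongest case against is that the planned test is valid and may be the better choice on the sponsor's own expectation. The SAP does not anticipate a period effect. Protocol section 6.0 repeats the same diet and study-day procedures in both periods, and section 4.0 excludes people with recent weight change. With no period effect, adjustment loses power in unstratified subgroups. It breaks even only at a period difference of roughly 30% of the Arg/Arg mean, and the larger gains need one of 65%. All of this stands, and it is why the point is only an improvement.

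Two further objections also stand. The SAP sizes the trial for race and gender effects, but its Data Analysis Plan specifies no subgroup test, so a reader should not infer that paired subgroup tests are planned. And stratification of order is unstated, not ruled out: the allocation schedule is not among the documents. If order is stratified by race and gender, the results averaged over uneven splits largely fall away.

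The objection does not dispose of the other cases. At full sample with balanced orders, adjustment is almost free, and it protects endpoints that lack the primary endpoint's spare power. Nor does it supply the missing consequence of the period test.

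**Conclusion.** The plan randomises drug order, analyses without it, and tests for a period effect to no stated end. This is worth changing because the change is cheap.

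A reader might infer that the primary analysis is biased or invalid. The documents do not support that. With balanced orders the paired test is unbiased and conservative. Averaged over unstratified splits its estimate is also unbiased, and its type I error is 3.9% to 5.0%. Inflation above 5% arises only conditionally, in a markedly uneven subgroup with a real period effect.

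The opposite inference, that the choice never matters at full sample, is also too broad. It holds for the primary endpoint at 3.76. At a half-SD period difference, power falls from 80% to 73% at an effect of 2.28, and from 86% to 80% for pAKT/AKT.

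These sizes rest on assumed period differences, a two-sided 0.05 test, normal differences, an assumed SD of 0.13 for the pAKT/AKT difference and, for the averaged subgroup figures, no stratification of order.

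**What to change.** State in the SAP that the main analysis is the Hills-Armitage period-adjusted treatment contrast, whatever the period test shows. Apply it to the primary and secondary endpoints and to any race or gender subgroup analysis. If a rank test is needed, use the rank-sum test of the period differences between the two orders. Keep the paired t-test or signed-rank test as a sensitivity analysis, and report the period test as descriptive.

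The change is to SAP wording only; it adds no subjects, visits or procedures. The statistical cost is one degree of freedom, plus some precision where orders are unequal. With no period effect, that is about 0.1 point of power or less at 17:17 (at pAKT/AKT, 86.15% to 86.09%), 0.3 points at 8:8 (86.3% to 86.0%), and 1.3 to 1.6 points in unstratified subgroups.

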Soluble epoxide hydrolase inhibitors are under development in humans. Among the pharmacological inhibitors of soluble epoxide hydrolase tested in rodents, the first to be tested in humans was 1-(1-acetyl-piperidin-4-yl)-3-adamantan-1-yl-urea or AR9281. A study of the effects of AR9281 in patients with hypertension and impaired glucose tolerance (NCT00847899) was completed, but not published. The sEH inhibitor GSK2256294 [(1R,3S)-N-(4-cyano-2-(trifluoromethyl)benzyl)-3-((4-methyl-6-(methylamino)-1,3,5-triazin-2-yl)amino)cyclohexanecarboxamide] has been studied safely in Phase I and II studies. The tmax is 0.5 hrs, and $t_{1/2}$ is 48 hrs. With multiple dosing in overweight smokers, steady-state was achieved within seven days. GSK2256294 10 mg achieved more than 95% inhibition of sEH throughout the dosing interval.

While sEH inhibition may have beneficial cardiovascular and renal effects in T2DM by improving endothelial function, ^{11,29} there could also be adverse consequences of long-term sEH inhibition. In pre-clinical models, EETs increase vascular endothelial growth factor (VEGF), increase proliferation and survival of endothelial cells, and promote angiogenesis, leading to metastasis of existing tumors.⁴² The effect of sEH inhibition on angiogenesis and tumor growth is complex, however. While EETs promote angiogenesis, other fatty acid substrates of sEH, such as the epoxydocosapentaenoic acids (from omega-3 fatty acids) reduce angiogenesis.⁴³ In some models, dual cyclooxygenase and sEH inhibition decreases angiogenesis and tumor growth.⁴⁴ In addition, chronic inflammation contributes to the development of many cancers, and the anti-inflammatory effects of EETs may prevent these. For example, sEH expression is increased in colon cancer; *Ephx2*-null mice are protected against dextran sulfate sodium-induced colitis and colon cancer.⁴⁵ There was no effect of sEH inhibitor GSK2256294 on circulating VEGF in Phase II studies.¹⁸ In this proof-of-concept study, we will treat patients with an sEH inhibitor for one week to avoid any risk of long-term effects.

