After completion of the study day, subjects will undergo a seven-week washout from study drug and then receive the opposite drug for one week, while eating the same standardized diet. On the seventh day of treatment they will report to the CRC after an overnight fast and repeat the study day protocol.

Standard Techniques

BP Measurements: During screening, washout, and active treatment outpatient BP will be measured with an aneroid sphygmomanometer (Welch Allyn, Skaneateles Falls, NY), using the appearance and complete disappearance of the Korotokoff sounds (K1 and K5) as systolic blood pressure (SBP) and diastolic blood pressure (DBP). The mean of three seated measurements will be used. During study days, BP will be measured every five min using an automated oscillometric recording device (Dinamap, Critikon, Carlsbad, CA).

Adipose harvest: Adipose tissue will be obtained from the periumbilical area using a TulipTM Medical closed syringe system for lipoaspiration (see Letter of Support). Under aseptic conditions and local lidocaine anesthesia, a small incision is made in the skin. The GEMS Johnnie Snap lock is placed into a 60-cc syringe, the Tulip liposuction cannula with 60-cc syringe attached is inserted at an angle through the incision to below Scarpa's fascia, and suction is applied until the syringe activates the clicker lock. The needle is moved in and out at a rate of approximately 1 Hz without breaking suction with a twisting motion. The sampling continues until approximately 5 g of tissue is removed (approximately 5.5 cc at a specific gravity of 0.918 for human fat). The syringe containing the sample will be taken on ice to the lab where it will be separated into pieces for measurement of sEH activity, DiHOME, EpOME, EETs, DNA and RNA isolation, adipocyte size and number, cytokines, and adipokines.

PBMC harvest: PBMCs will be obtained through the peripheral IV into 3 EDTA tubes for total of 12 milliliters, and transported at room temperature to the lab for processing. Cells will then be passed through a Ficoll-Paque barrier, washed with PBS, and stored in DMSO.

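### After a positive carry-over test the SAP lets the primary analysis use period 1 alone or both periods, with no test level and no rule; switching to period 1 raises type I error from 5% to about 7.4–8.2%

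*SAP*

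**What the plan says.** The primary comparison is GSK2256294 versus placebo on insulin sensitivity in a two-period crossover. The SAP's Data Analysis Plan specifies a paired t-test or a Wilcoxon signed-rank test and then turns to carry-over:

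- Expectation: "We do not expect a carry-over effect with the eight-week period between study days".
- Test: "we will test for a carryover effect using the T-test approach proposed by Jones and Kenward".
- If positive, first option: "Should a carry over effect exist, we will either use period one data to estimate the treatment effect".
- If positive, second option: "or estimate the treatment effect using data from both periods", accepting that carry-over may bias the estimate downwards.
- Period effect: "we will use the T-test approach of Hills and Armitage to test for one". No consequence of that test is stated.

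Neither document gives a level for the carry-over test or says which option applies when. The planned error rate is in the sample-size paragraph: "with 80% power and 0.05 type 1 error rate with 34 subjects". Protocol section 6.0 says that "subjects will undergo a seven-week washout from study drug", and section 1.0 gives a half-life of 48 hours.

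**The concern.** A preliminary test that can change the primary estimator is harmless only if it is unrelated to the estimate it leads to. Here it is closely related. The carry-over test compares subject totals (period 1 plus period 2) between the two sequences, and the period-1 estimate is one component of those totals. When there is no carry-over, a positive result is often produced by a chance imbalance in period 1, and the plan then allows that same imbalance to be tested as the treatment effect.

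The open choice adds to this. With no rule, the team can decide between two estimates after seeing both. Two things are at stake: the 0.05 error rate of the primary test, and the accuracy of the reported effect in any trial where the switch is made.

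**Working it through.** **Inputs.** From the SAP: 34 subjects, error rate 0.05, within-subject correlation r = 0.5, SD of the within-subject difference 4.6, planning difference 3.76. At r = 0.5 the single-period SD is also 4.6, because 4.6 × √(2 × (1 − 0.5)) = 4.6. Assumed: two-sided testing, 17 per sequence (the protocol states permuted blocks but no ratio), normal data, and a carry-over test level of 5% or 10%.

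**The plan's own power figure.** SE = 4.6/√34 = 0.79, and 3.76/0.79 ≈ 4.8 standard errors. A paired t-test then has 99.6% power, not 80%; the difference detectable with 80% power is 2.28. This mismatch is a separate matter and does not affect the type I error below. The SAP's figure for 16 subjects does reproduce (86.3% against 86%).

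**Correlation of the two contrasts.** corr(totals contrast, period-1 contrast) = √((1 + r)/2) = √0.75 = 0.87. Totals and within-subject differences are independent, so a positive carry-over test says nothing about the two-period estimate but a great deal about the period-1 estimate.

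**Type I error when period 1 is always used after a positive test.** Error = P(test negative) × 0.05 + P(test positive) × P(period-1 test significant | test positive). By normal theory the last term is 0.533 at the 5% level and 0.370 at the 10% level.

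- 5% level: 0.95 × 0.05 + 0.05 × 0.533 = 0.0475 + 0.0266 = 7.4%
- 10% level: 0.90 × 0.05 + 0.10 × 0.370 = 0.0450 + 0.0370 = 8.2%

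Simulation with t-tests and 17 per sequence (at least 200,000 trials per setting) agrees:

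| Rule after a positive carry-over test | 5% level | 10% level |
|---|---|---|
| Always keep both periods | 5.0% | 5.0% |
| Switch to period 1 | 7.3–7.4% | 8.0–8.2% |
| Report the more favourable | 7.4–7.5% | 8.3–8.4% |

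For r from 0.3 to 0.8 the switch gives about 7–8% and 8–9%. At a 1% level it gives 5.7–5.8%.

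**What happens after a false alarm** (r = 0.5, no true effects). Standard errors: period 1, 4.6 × √(2/17) = 1.58; both periods, 0.79.

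| Given a positive test | 5% level | 10% level |
|---|---|---|
| Period-1 test falsely significant | 52% | 36–37% |
| Period-1 95% interval covers the truth | 48% | 63–64% |
| Mean absolute error, period 1 | 3.1 | 2.8 |

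At the 5% level the mean absolute error from both periods is 0.63, and the two-period test is falsely significant 4.8% of the time. Over all trials, coverage of the two-stage interval at the 5% level is 0.95 × 0.95 + 0.05 × 0.483 = 92.7%, and mean absolute error is 0.95 × 0.63 + 0.05 × 3.10 = 0.75.

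**Power.** At 3.76, power falls from 99.6% to about 97% (5% level) or 95% (10% level). At 2.28 it falls from 80% to about 78.5% or 77%.

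**Is a positive test likely to be real?** Seven weeks is 49 days, and 49/2 = 24.5 half-lives, so the drug itself is cleared. The documents do not show how long any effect on insulin sensitivity lasts. Negligible carry-over is therefore a reasonable assumption, not a demonstrated fact.

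**Period effect.** With balanced sequences the unadjusted paired test does not inflate type I error, but it becomes conservative. For an assumed period shift of 2.3 its type I error is 2.9% and its power at 2.28 is 72.6%, against 80% when adjusted. Adjusting for period while keeping the carry-over gate still gives 7.3% and 8.2%, so adjustment alone does not solve the problem.

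**The case against.** Four points deserve weight.

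1. **The inflation is conditional.** It needs an assumed test level and a decision to switch. A team that always kept both periods would stay at 5.0%, and a 1% test level would give under 6%. This stands as a limit on the size. It does not answer the point, because the SAP commits to neither.

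2. **The worst figures follow a rare event.** The 52% and 48% apply only after a false alarm, 1 null trial in 20 at the 5% level; averaged over all trials the loss is modest. The 3.1-unit error also scales with the SD. At the 1.3 that the SAP reports for Arg/Arg homozygotes it would be 3.1 × 1.3/4.6 = 0.88, although the type I error would not change. Both remarks are correct.

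3. **Real carry-over would bias the two-period estimate.** Suppose a treatment effect of 3.76 and a carry-over of half that, 1.88. The two-period estimate is then biased by −1.88/2 = −0.94, and its 95% interval covers about 80%. The gate does not repair this; coverage of the two-stage rule is also about 80%. The SE of the totals contrast is 4.6 × √3 × √(2/17) = 2.73, so 1.88 is only 0.69 standard errors, and a 5% test detects it in roughly 10% of trials. This is a reason to show period-1 results as a sensitivity analysis, not to let them replace the primary result.

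4. **This is a proof-of-concept study with ample power.** Power does not protect the type I error rate, and the cost of correction is close to nil.

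**Conclusion.** The concern holds. The SAP makes the primary estimator depend on a carry-over test with no stated level and leaves two options open with no rule. Under the SAP's correlation of 0.5, with 17 per sequence, normal data, no true carry-over and a switch to period 1 after every positive test, type I error is about 7.4% at an assumed 5% test level and 8.2% at 10%, against the planned 5%. The excess belongs to the period-1 branch and to the undefined choice; the two-period analysis on its own keeps 5%. The overall power loss is small. Because the defect affects the error rate and pre-specification of the primary test, it should be corrected before the data are analysed. The missing consequence of the period-effect test is a secondary point: it costs some power if a period effect occurs, but does not inflate the error rate.

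**What to change.** In the SAP's Data Analysis Plan, remove the carry-over test as a decision step and drop period 1 as an alternative primary analysis. Suggested wording:

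> Whatever the carry-over and period results, the primary analysis is the period-adjusted treatment estimate from both periods (Hills–Armitage treatment t-test, two-sided 0.05). Carry-over is assumed negligible because of the seven-week washout; its estimate and 95% interval are reported descriptively and do not alter the primary analysis. A period-1 comparison and a rank-based test are sensitivity analyses only.

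A mixed model with treatment, period and sequence as fixed effects and subject as random gives the same answer on complete data, and Protocol section 5.0 replaces non-completers. Either could serve, but the SAP should name one.

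The cost is wording and one degree of freedom (33 to 32). The difference detectable with 80% power moves from 2.277 to 2.279. No extra subjects or data are needed.
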